E. Significance: How will this change our practice, increase our national standing, attract patients or advance our knowledge about CV disease. What is Mayo unique? (numbered list).

- 1) Cardio-oncology is a rapidly expanding field and Mayo Clinic has several clinicians at the forefront¹⁰
- 2) Oncologic patients are attracted to Mayo Clinic already for our expertise and this will further enhance the practice
- 3) Mayo Clinic is a leading center for cardiac PET and specifically PET-CT MFR⁶

E. Brief Synopsis of Methods: Very brief summary – numbered list acceptable – of what will actually be done.

- 1) Collaboration between Cardiology, Oncology and Cardiac PET to recruit 6 consecutive patients beginning ICI therapy
- 2) Screening labs, including troponin, high sensitivity CRP, and **NT-proBNP**; peripheral blood draw sent to research lab ([name]) for T cell phenotyping.
- 3) Complete PET-CT MFR⁶ immediately before and 4-6 weeks after initiation of ICIs
- 4) Assess change in MFR (per literature 20% or more decreased indicates significant change)⁷
- 5) Continue long-term follow-up of the patients in charts to determine if any develop IRAEs
- 6) For patients who develop myocarditis a FDG PET-CT would be performed to assess for inflammation

E.1 Detailed Methods

1) Recruitment: Investigator [name] has met with hematology team ([name] MD PhD) who will work with his PA team to identify eligible patients for recruitment. Those deemed eligible will be approached during their initial visits with oncology (prior to initiation of ICI.

2): PET-CT MFR methodology (performed during two sessions-one before and one 4-6 weeks after administration of ICI):

A GE Discovery 690XT, Discovery Molecular Insights (DMI) or 710 PET/CT system (GE Healthcare, Waukesha, WI) will be utilized in performing the studies. The imaging system consists of full ring Cerium-doped Lutetium Yttrium Orthosilicate (LYSO) crystals. 128x128 PET matrix size with zoomed 41.9 cm field of view centered over the heart will be used to obtain the PET images. Furthermore, three-dimensional list mode acquisition will be employed. Three-dimensional iterative reconstruction algorithm with time-of-flight correction, CT attenuation, scatter, randoms, normalization, decay and dead time correction will be utilized. Three-dimensional Hanning post-filter with a 10 mm cut-off will also be used.

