Continuous data (e.g., age) will be summarized using the following descriptive summary statistics: the number of subjects (n), mean, SD, median, minimum value (min), and maximum value (max). For each continuous variable, the corresponding mean, median, minimum and maximum will be presented to 1 decimal place and the SD to 2 decimal places, unless otherwise specified.

Categorical variables (e.g., qualitative presence or absence of perfusion deficit) will be summarized using counts and percentages. Percentages will be presented to 1 decimal place. Summaries of continuous and categorical data will be presented, as appropriate.

Incomplete/Missing data: Missing data (e.g., dates, post-baseline values) will not be imputed, unless otherwise specified; i.e., all missing values and missing post-baseline values will remain as missing in all statistical analyses and listings, unless otherwise specified.

Outliers: No formal statistical analyses will be performed to detect and/or remedy the presence of statistical outliers.

Additionally, all subject data, including derived variables, will be presented in subject data listings; listings will display all subjects who were randomized or enrolled in the study.

Background Characteristics

Demographics and Baseline Characteristics

Demographics and baseline characteristics (age, sex, race, ethnicity, weight, height and body mass index [BMI]) will be summarized.

Efficacy Analysis

Analysis of Primary Efficacy Endpoint

Nominal continuous variables will be represented as the mean +/- SD and categorical variables will be noted as the number and percentage of total. Pearson chi-square test will be utilized to determine statistical significance for continuous variables whereas a Student's two-sample t-test will be implemented to determine statistical significance for categorical variables. Univariate and multivariate analyses will be performed when relevant. Statistical significance will be set a priori as a p-value less than 0.05. Given that this is a pilot study no power calculation will be performed. All statistical analyses will be performed using JMP Pro 9 (SAS Institute INC. Cary, North Carolina).

Adverse Events Collection:

Adverse Events will be collected only for activities done for research.

The selection of study subjects will be based upon the following inclusion and exclusion criteria:

Inclusion

1. First time administration of ICI
2. Willing and able to return in 4-6 weeks for follow-up study

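### Once the swapped tests are put right, Pearson chi-square p-values are still unreliable for categorical data in six patients; the plan should name exact tests, paired for before/after comparisons

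*Combined protocol and SAP*

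**What the plan says.** The Brief Synopsis of Methods (item 1) plans to "recruit 6 consecutive patients beginning ICI therapy". Item 3 has each of them scanned "immediately before and 4-6 weeks after initiation of ICIs", so every imaging variable is paired within patient. Item 4 gives a threshold for change in myocardial flow reserve (MFR): "per literature 20% or more decreased indicates significant change".

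Under Statistical Analysis, General Considerations gives "qualitative presence or absence of perfusion deficit" as its example of a categorical variable, to be summarised by counts and percentages. The paragraph on the primary efficacy endpoint then names two tests: "Pearson chi-square test will be utilized to determine statistical significance", which the sentence goes on to attach to continuous variables, and "Student's two-sample t-test will be implemented to determine statistical significance for categorical variables". It adds unspecified univariate and multivariate analyses and the rule "Statistical significance will be set a priori as a p-value less than 0.05". It does not say whether tests are one- or two-sided or which categorical variables are to be compared. No exact test, paired test, continuity correction or small-count rule appears anywhere.

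**The concern.** As written, the two tests are attached to the wrong variable types. The natural repair is to exchange them and stop there. That would leave Pearson chi-square as the only test for categorical data, and its p-value is a large-sample approximation applied here to six people.

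The reported p-value for a particular table could then be far smaller than an exact calculation supports, and the 0.05 rule would label it significant. The Aims describe the study as a pilot for larger trials, so a p-value that rests on one coincident patient could shape what is studied next. Before/after comparisons raise a second and distinct problem: an ordinary chi-square treats the two scans of one patient as if they came from different patients.

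**Working it through.** The plan gives no power or test result to reproduce, so the check is a full enumeration.

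**Inputs.** N = 6 and two scans per patient (Brief Synopsis, items 1 and 3); significance at 0.05 (Analysis of Primary Efficacy Endpoint). Assumptions: two-sided tests, chi-square without continuity correction, and the swapped variable types corrected.

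**1. Expected counts, between-patient 2x2 table.** Expected count = row total × column total / 6. The largest possible value is 5 × 5 / 6 = 4.17, so no cell of any such table reaches 5.

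**2. Pearson.** For a table with cells a, b, c, d,

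X² = 6(ad − bc)² / [(a+b)(c+d)(a+c)(b+d)].

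For a perfectly aligned table with split r v (6 − r), b = c = 0, so X² = 6[r(6 − r)]² / [r(6 − r)]² = 6 whatever r is, and P(χ² on 1 df > 6) = 0.0143. Across all tables of six with non-zero margins, these are the only ones below 0.05; the next smallest Pearson p is 0.083 (X² = 3).

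**3. Exact p-values for the same tables.** Fisher's test conditions on both margins. The Barnard and Boschloo tests fix the group sizes only.

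| Split | Pearson | Fisher | Barnard | Boschloo |
|---|---|---|---|---|
| 2 v 4 | 0.0143 | 1/15 = 0.067 | 0.031 | 0.044 |
| 3 v 3 | 0.0143 | 2/20 = 0.100 | 0.031 | 0.031 |
| 1 v 5 | 0.0143 | 1/6 = 0.167 | 0.067 | 0.134 |

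The smallest Fisher p in any between-patient 2x2 table of six is 0.067. Fisher exceeds Pearson by a factor of 0.067/0.0143 = 4.7 to 0.167/0.0143 = 11.7.

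**4. Overall false-positive rate of the rule Pearson p < 0.05.** With neither margin fixed, as in this single-group study, the maximum over all pairs of prevalences is 3.1%. With group sizes fixed, the maximum is 3.1% for 2 v 4 and 3 v 3, and 6.7% for 1 v 5. Conditional on matching margins the rate equals the Fisher p above (6.7%, 10.0%, 16.7%); for margins that do not match it is 0.

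**5. Before/after perfusion deficit, all changes in one direction.** Pearson treats the scans as 6 v 6 independent readings. Exact McNemar uses the k patients who changed: p = 2 × 0.5^k.

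| Before to after | Pearson | Exact McNemar |
|---|---|---|
| 0/6 to 3/6 | 0.046 | 2 × 0.5³ = 0.25 |
| 0/6 to 4/6 | 0.014 | 2 × 0.5⁴ = 0.125 |
| 0/6 to 5/6 | 0.003 | 2 × 0.5⁵ = 0.063 |
| 0/6 to 6/6 | 0.0005 | 2 × 0.5⁶ = 0.031 |

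Only when all six patients change in the same direction does the paired exact p fall below 0.05.

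**6. Missing scans.** Values are not imputed, so N can fall. At N = 5 an aligned between-patient table gives Pearson 0.025 against Fisher 0.10 to 0.20; at N = 4, 0.046 against 0.25 to 0.33.

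**The case against.** A reader might infer that chi-square here produces false positives well above 5%, or that no exact method could support any between-patient result. Neither follows. The plan fixes neither margin of a between-patient table, and on that footing the rule errs at most 3.1% of the time. Fisher's test is conservative at this size, and for the 2 v 4 and 3 v 3 tables the accepted unconditional exact tests fall below 0.05. For those two patterns the verdict at 0.05 depends on which exact method is chosen. Only the 1 v 5 table stays above 0.05 under every exact test tried.

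The comparison is also hypothetical. The plan attaches chi-square to continuous variables, attaches no test to perfusion deficit, and defines no marker-positive group. D. Innovation asks about correlation with T cell phenotypes, and inclusion criterion 3 says that the change in MFR, a continuous quantity, is what is assessed. A marker-by-decliner table is a plausible use of the 20% threshold but is not a planned one.

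Finally, the before/after gaps combine ignored pairing with small counts and cannot be used to size the small-sample problem alone.

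All of this stands and limits the point. What survives is that the plan supplies no exact or paired method for categorical data, and that every between-patient table Pearson would call significant carries a p-value smaller than any exact test computed here gives.

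**Conclusion.** The point holds in a limited form. If the swap is corrected and chi-square is applied to categorical data, the p-value reported for an aligned between-patient table is too small: 0.0143 against 0.067 to 0.167 by Fisher's test, or 0.031 to 0.134 by the unconditional exact tests. The clearest error is the 1 v 5 table, where one patient who happens to be positive on both variables gives p = 0.014 although, given those margins, the match has a chance of 1 in 6. The documents do not support a claim of general error inflation.

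The separate pairing problem changes the conclusion at 0.05 for one-directional changes from 0/6 to 3/6, 4/6 or 5/6.

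These results rest on two-sided tests, no continuity correction, all six patients contributing, and categorical comparisons being made at all, which the plan implies by naming a test for categorical variables but does not specify.

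**What to change.** Rewrite the test sentence in the primary-efficacy paragraph as a whole. Changing only the name of the chi-square test would leave exact categorical tests assigned to continuous variables and the t-test assigned to categorical ones. In the rewrite:

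- Correct the swapped variable types.
- Report categorical variables as counts and percentages.
- Take any p-value shown for a between-patient 2x2 table from Fisher's exact test.
- Use the exact McNemar test for any before/after categorical comparison, in patients with both scans.
- State that between-patient 2x2 results are descriptive, with no significance claim even where a p-value is shown, because Fisher's p cannot fall below 0.067 with six patients.

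The cost is a few lines of text, with no new data or visits. The downside is that p-values become less favourable and that Fisher's test is conservative. If the investigators prefer an unconditional exact test, they should name it before seeing the data, since the 2 v 4 and 3 v 3 verdicts depend on that choice and the statement that these tables are descriptive would then need its own justification.
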